4.7. Randomization Criteria

Participants will be randomized after successfully meeting all eligibility requirements.

4.8. Lifestyle Requirements

In order to participate in the study, participants must be aware of the life style guidelines and restrictions that apply during and after the study period described in Section 4.8.2 and Appendix 25.

4.8.1. Surgery

During the study, no elective surgery should occur without first consulting with the sponsor. Preferably, elective surgery should occur 4 weeks before the study screening visit or be delayed until participation in the study is completed.

The sponsor should be notified if a participant requires surgery (including dental surgery) during the study to determine whether the participant should discontinue from the study and/or discontinue the investigational product prior to the surgical procedure. In general, planned surgical procedures should not be performed unless the investigational product has been discontinued for at least 28 days (unless otherwise advised by the sponsor). In addition, the sponsor should be notified as soon as possible if a participant undergoes a surgical procedure without first informing the study staff.

4.8.2. Contraception

Studies to evaluate the development toxicity of PF-06823859 have not been conducted. Therefore, the use of a highly effective method of contraception is required (see Appendix 25 and study sites participating in Germany please see Appendix 24).

The investigator or his or her designee, in consultation with the participant, will confirm that the participant has selected an appropriate method of contraception for the individual participant and his or her partner(s) from the permitted list of contraception methods (see Appendix 25 and study sites from Germany see Appendix 24) and will confirm that the participant has been instructed in its consistent and correct use. At time points indicated in the SoA, the investigator or designee will inform the participant of the need to use highly effective contraception consistently and correctly and document the conversation and the participant's affirmation in the participant's chart (participants need to affirm their consistent and correct use of at least 1 of the selected methods of contraception) considering that their risk for pregnancy may have changed since the last visit. In addition, the investigator or designee will instruct the participant to call immediately if the selected contraception method is discontinued or if pregnancy is known or suspected in the participant or partner.

In Germany, CTFG guidelines will be followed, where one highly effective method of contraception must be used, see Appendix 24. The investigator will document the conversation, and the participant's affirmation, in the participant's chart.

4.9. Sponsor's Qualified Medical Personnel

The contact information for the sponsor's appropriately qualified medical personnel for the study is documented in the study contact list located in Study Team on Demand (STOD), [contact].

To facilitate access to appropriately qualified medical personnel on study-related medical questions or problems, participants are provided with a contact card. The contact card contains, at a minimum, protocol and investigational product identifiers, participant study numbers, contact information for the investigator site, and contact details for a contact center in the event that the investigator site staff cannot be reached to provide advice on a medical question or problem originating from another healthcare professional not involved in the participant's participation in the study. The contact number can also be used by investigator staff if they are seeking advice on medical questions or problems; however, it should be used only in the event that the established communication pathways between the investigator site and the study team are not available. It is therefore intended to augment, but not replace, the established communication pathways between the investigator site and the study team for advice on medical questions or problems that may arise during the study. The contact number is not intended for use by the participant directly, and if a participant calls that number, he or she will be directed back to the investigator site.

5. STUDY TREATMENTS

For the purposes of this study, and per International Conference on Harmonisation (ICH) guidelines, investigational product is defined as a pharmaceutical form of an active ingredient or placebo being tested or used as a reference/comparator in a clinical trial, including a product with a marketing authorization when used or assembled (formulated or packaged) in a way different from the approved form, or when used for an unapproved indication, or when used to gain further information about an approved use (ICH E6 1.33).

For this study, the investigational product will be administered intravenously over approximately one hour. Investigational product will be administered every 4 weeks, each participant receiving 3 doses of investigational product.

5.1. Allocation to Treatment

Allocation of participants to treatment/ or placebo will proceed through the use of an interactive response technology (IRT) system or (interactive Web-based response [IWR]. The blinded personnel will be required to enter or select information including but not limited to the user's identification (ID) and password, the protocol number and the participant number. The blinded person will then be provided with a randomization number, and dispensable unit (DU) or container number when investigational product is being supplied via the IRT system. It is noted that all of the information shown in the IRT system during drug assignment, and on the relevant confirmation report, is blinded information. The IRT system will provide a confirmation report containing the participant number, randomization number, and DU or container number assigned.

The study specific IRT reference manual will provide the contact information and further details on the use of the IRT system.

5.2. Breaking the Blind

This study will be double blinded, (Sponsor, Investigator and participant will all be and remain blinded throughout the duration of the study). An interim analysis may be conducted for internal decision making. An internal review committee, (IRC) separate from the blinded study team will review safety and efficacy data.

At the initiation of the study, the investigator site will be instructed on the method for breaking the blind. The method will be an electronic process. Blinding codes are able to be broken in exceptional circumstances when knowledge of the actual treatment code is absolutely essential for further management of the participant. If the situation allows, investigators are encouraged to discuss with the sponsor's medical monitor if they believe unblinding is necessary, however, under no circumstances should unblinding be delayed in an emergency situation. When the blinding code is broken, the reason must be fully documented and entered on the case report form (CRF).

5.3. Participant Compliance

All doses of investigational product will be administered by the appropriately designated study staff at the investigator site.

5.4. Investigational Product Supplies

5.4.1. Dosage Form(s) and Packaging

CCI	
Placebo for CCI	
	sealed with a stopper and a flip off
aluminum seal.	_

The vials will be packed into cartons containing 6 vials per carton.

5.4.2. Preparation and Dispensing

Once eligibility has been confirmed through the screening period process, each participant will be randomized. The investigational product will be dispensed using an interactive response technology, (IRT) drug management system at each dispensing visit. A qualified staff member will dispense the investigational product via unique container numbers on the label provided, in quantities appropriate for the dose assignment.

See the IP manual for instructions on how to prepare the investigational product for administration. Investigational product should be prepared and dispensed by an appropriately qualified and experienced member of the study staff (eg, physician, nurse, physician's assistant, nurse practitioner, pharmacy assistant/technician, or pharmacist) as allowed by local, state, and institutional guidance.

PF-06823859 doses and placebo will be prepared by qualified unblinded site personnel according to the IP manual. The investigational product will be administered to participants in a blinded manner.

5.5. Administration

Blinded IV PF-06823859 or placebo will be administered at the investigative site or clinic over the course of CCI

has completed, all participants will be monitored for an additional 60 minutes post investigational treatment administration.

5.5.1. Infusion Discontinuation

- If a participant experiences symptoms typical of an allergic reaction, the study drug administration should be discontinued immediately and permanently.
- If a participant experiences symptoms typical of infusion reactions (eg, lightheadedness, nausea, chills, fever), the study drug infusion should be stopped. At the discretion of the investigator, the infusion can be restarted at a slower rate if symptoms are resolved within 1 hour after the stop of infusion. If symptoms return,

then the study drug administration should be discontinued immediately and permanently.

• In the event that there is an infusion interruption, the entire duration of drug infusion, from the initial start of infusion to the completion of infusion, should not exceed 3 hours. Participants will receive appropriate treatment at the discretion of the investigator.

5.6. Investigational Product Storage

The investigator, or an approved representative, eg, pharmacist, will ensure that all investigational products are stored in a secured area with controlled access under required storage conditions and in accordance with applicable regulatory requirements.

Investigational product should be stored in its original container and in accordance with the label.

See the IP manual for complete information on storage conditions, handling and stability of the product.

Any storage conditions stated in the single reference safety document (SRSD) (eg, Investigator's Brochure [IB]) will be superseded by the storage conditions stated on the product label.

Site systems must be capable of measuring and documenting (for example, via a log), at a minimum, daily minimum and maximum temperatures for all site storage locations (as applicable, including frozen, refrigerated, and/or room temperature products). This should be captured from the time of investigational product receipt throughout the study. Even for continuous monitoring systems, a log or site procedure that ensures daily evaluation for excursions should be available. The intent is to ensure that the minimum and maximum temperature is checked each business day to confirm that no excursion occurred since the last evaluation and to provide the site with the capability to store or view the minimum/maximum temperature for all nonworking days upon return to normal operations. The operation of the temperature monitoring device and storage unit (for example, refrigerator), as applicable, should be regularly inspected to ensure it is maintained in working order.

Any excursions from the product label storage conditions should be reported to Pfizer upon discovery. The site should actively pursue options for returning the product to the storage conditions as described in the labeling, as soon as possible. Deviations from the storage requirements, including any actions taken, must be documented and reported to Pfizer.

Once an excursion is identified, the investigational product must be quarantined and not used until Pfizer provides documentation of permission to use the investigational product. It will not be considered a protocol deviation if Pfizer approves the use of the investigational product after the temperature excursion. Use of the investigational product prior to Pfizer approval will be considered a protocol deviation. Specific details regarding information the site should report for each excursion will be provided to the site. Receipt of materials, door opening and closing, and other routine handling operations where the product(s) are briefly out of the temperature range described in the labeling are not considered excursions.

5.7. Investigational Product Accountability

The investigator site must maintain adequate records documenting the receipt, use, loss, or other disposition of the investigational product supplies. All investigational products will be accounted for using a drug accountability form/record.

5.7.1. Destruction of Investigational Product Supplies

The sponsor or designee will provide guidance on the destruction of unused investigational product (eg, at the site). If destruction is authorized to take place at the investigator site, the investigator must ensure that the materials are destroyed in compliance with applicable environmental regulations, institutional policy, and any special instructions provided by Pfizer, and all destruction must be adequately documented.

All used glass vials should be maintained at the investigative site for accountability. The investigator will maintain the unused supply until destruction is authorized. Pfizer will provide instructions as to the disposition of any unused investigational product.

5.8. Concomitant Treatment(s)

5.8.1. Prior Treatments

The indication for use, total daily dose, route of administration, and start and stop dates for all prior medications (including prescription medications and treatments, vaccinations, nonprescription medications, nondrug treatments and dietary supplements) received within 30 days prior to obtaining informed consent for the study will be recorded on the CRF.

For a list of prohibited and permitted concomitant medications refer to Appendix 15 and Appendix 16 Concomitant Treatment(s)

Participants will abstain from concomitant treatments as described in the Inclusion and Exclusion sections of the protocol.

Participants enrolling in the study are permitted to be on a stable DM treatment prior to Day 1 investigational treatment, as long as it is permitted treatment. All concomitant treatments taken during the study must be recorded in study records with indication for use, total daily dose, and start and stop dates of administration.

All participants will be questioned about concomitant treatment at each site visit.

Medications that are taken during the 5-week screening period (after informed consent is obtained and before the first dose of investigational product) will be documented as prior medications. Medications taken after the first dose of investigational product has been administered will be documented as concomitant medications.

Participants will be asked about all concomitant treatments (including prescription medications and treatments, vaccinations, nonprescription medications, nondrug treatments, dietary supplements and herbal preparations) at each study visit. Any new concomitant medications or dose changes to current concomitant medications should be evaluated for potential new or worsening AEs.

For the purposes of this protocol, dietary supplements are defined as vitamins, minerals, purified food substances, and herbals with pharmaceutical properties. Vitamins, minerals, purified food substances, and herbals with pharmaceutical properties are allowed in amounts not known to be associated with adverse effects (such as hypervitaminosis). Herbals with unknown properties or those herbals that are known to have an effect on drug metabolism (eg, St. John's Wort) must be discontinued at least 1 week or 5 half-lives (whichever is longer) before the first dose of investigational product.

5.8.2. Prohibited Concomitant Medications

Please See Appendix 15 and Appendix 16.

5.8.3. Permitted Concomitant Medications

Please See Appendix 15 and Appendix 16.

5.8.4. Pre Medication use on the day of IVIG Administration

For participants who enroll in the study who are on IVIG: On the day of IVIG dose administration, pre-medication to prevent hypersensitivity reaction to IVIG is permitted. The steroid dose that was previously used for pre-medication will be permitted (on IVIG dosing day only). After IVIG dosing day, steroid dosing should remain less than or equal to 15 mg or equivalent per day as per protocol Section 5.8.5.

There is no need to change the IVIG dosing schedule or adjust the IVIG dosing schedule related to investigational product administration.

5.8.5. Corticosteroids

For Stage 1, 2, a stable dose of ≤ 15 mg/day of corticosteroids or equivalent are permitted during the study through Week 12, Visit 6. After Week 12 as per the investigator's discretion tapering of steroids may occur. The decision of tapering the steroids is entirely up to the study investigator and any change in the steroid dose should be recorded on the concomitant steroid page.

For Amended Stage 2, a stable dose of ≤ 15 mg/day of corticosteroids or equivalent are permitted during the study through Week 24, Visit 9. After Week 24 as per the investigator's discretion tapering of steroids may occur. The decision of tapering the steroids is entirely up to the study investigator and any change in the steroid dose should be recorded on the concomitant steroid page. Please note if the participant is considering entering the open label extension study, please refrain from tapering steroids until the participant has been in the open label study for 4 weeks. For Stage 3, a stable dose of ≤ 20 mg/day of corticosteroid's or equivalent are permitted during the study through Week 24, Visit 9. After Week 24 as per the investigator's discretion tapering of steroids may occur. The decision of tapering the steroids is entirely up to the study investigator and any change in the steroid dose should be recorded on the concomitant steroid page. Please note if the participant is considering entering the open label extension study, please refrain from tapering steroids until the participant has been in the open label study for 4 weeks.

All concomitant treatments including corticosteroids or equivalent taken during the study must be recorded in study records with indication for use, total daily dose, and start and stop dates of administration.

5.8.6. Guidance for Investigators

During the course of the study, those participant who experience a severe flare requiring new or increased doses of immunosuppressants (including new or increased doses of corticosteroids beyond what is permitted or hospitalization), will be discontinued from the treatment period of the study and placed in the follow-up period, and therefore, will receive no further investigational product. Rescue therapy may be administered as clinically necessary.

5.9. Rescue Medication

After a participant enters the follow up period, or prematurely withdrawn from the study for any reason, medically necessary treatments for DM will be allowed. The previous prohibited medications will no longer apply.

6. STUDY PROCEDURES

6.1. Screening

For screening procedures, see Schedule of Activities and ASSESSMENTS section.

Participants will be screened within 35 days prior to administration of investigational product to confirm that they meet the participant eligibility criteria for the study. The investigator (or appropriate delegate at the investigator site) will obtain informed consent from each participant in accordance with the procedures described in Section 12.3. Screening visits may occur over multiple visits to achieve all of the required testing.

Screening laboratory tests with abnormal results may be repeated once to confirm abnormal results. The last value (most recent value obtained) will be used to determine eligibility. If results return to normal within the 5-week screening period, the participant may enter the study.

Rescreening:

Participants who do not meet the eligibility criteria (ie, screen failure) may be re-screened once at a later date. Any participant who is re-screened must be re-consented and receive a new participant number. All activities required for the screening visit must be repeated.

6.2. Study Period

6.2.1. Treatment Period (Stage 1 and 2)

The treatment period will begin on Day 1 and consist of 4 scheduled visits, (Visits 2-5). From Day 1, where investigational treatment or placebo is received, a scheduled visit will occur in 7 days (\pm) 3 days, to follow up with the participant after the first investigational drug/placebo administration. For all other visits the participant will be seen every 4 weeks from Day 1. Investigational treatment will be received at Visits 2 (Day 1), Visits 4 and 5. During the treatment period visits, the following assessments may occur:

- Investigational drug or placebo administered.
- Skin biopsy (4). (*After randomization prior to first dose of investigational/placebo treatment*) Day 1, Visit 2.
- CDASI assessment.
- CCI
- Physicians Global Assessment.
- Vital signs, (Blood pressure, (BP), Heart Rate, (HR), Pulse, respirations and temperature).
- Weight.
- Targeted Physical examination.
- ECG, (Day 1, Visits 4, 5, 6, End of Study or Early termination).
- Blood & urine collection for safety laboratory testing.
- Males and females, (contraception check).
- All females Urine Pregnancy test.
- Blood collection for various biomarkers, (IP-10, MX-A, CCI hsCRP, Gene signature panel).
- **CC**
- CCI
- Patient reported outcomes, 5D Pruritus Scale, SF36 V2 Acute, and DLQI.
- Recording of any new concomitant medications, DM concomitant medications or changes in ongoing concomitant medications, or DM concomitant medications.

- Collection for Viral Surveillance.
- Check for Infusion site reactions.
- Collection of any serious and non-serious adverse events.
- Genomic Banked biospecimen (Prep D1) If missed, the site may collect at the next available time point when biospecimens are being collected in conjunction with a participant visit.

Please see the Schedule of Assessments for specific details on which procedures will occur at each visit.

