3. STUDY DESIGN

3.1. Study Overview

Stage 1 was a multi-center Phase 2A study planned to be conducted in approximately 30 adult participants with moderate to severe DM. Thirty two participants were randomized in order to collect data from 24 participants who completed the study. Each participant was to take part in the study for a period of approximately 9 months. After the 35 day screening period, participants who were eligible enrolled into the study and were randomized in a blinded manner, 2:1 (Active:Placebo) ratio. Investigational drug or placebo administration took place on Day 1, Week 4 and Week 8 of the study. Participants then entered a 5-month follow-up period.

In Stage 2, with the addition of 1 lower dose arm, this study then became a CCI

Participants will receive study drug, (active or placebo) on Day 1, Week 4, (Visit 4), and Week 8, (Visit 5). At Week 12, (Visit 6) is the scheduled primary endpoint of the study.

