The treatment period will begin on Day 1 and consist of 8 scheduled visits, (Visits 2-8). The first dose of investigational treatment or placebo will be administered on Day 1. Following Day 1, a scheduled visit will occur in 7 days (\pm) 3 days. Otherwise, monthly visits will occur to the end of the follow-up period after the first dose administration. Investigational treatment will be received at Visit 2 (Day 1), Visit 4 (Week 4), Visit 5 (Week 8), Visit 6 (Week 12), Visit 7 (Week 16) and Visit 8 (Week 20). The end of the treatment period is at Week 24. Once Week 24 has been completed, eligible participants will have the opportunity to enter the open label extension study or they may continue into the follow up period.

During the treatment period visits, the following assessments may occur: For more details please follow the SoA.

- Investigational drug or placebo administered through Visit 8.
- CDASI assessment.
- CCI
- MMT-8 assessment (See Appendix 21).
- Physicians Global Assessment, PhGA, VAS (See Appendix 3).
- Myositis Disease Activity Assessment Test, MDAAT(See Appendix 20).
- Recording of Muscle Enzymes (See Appendix 19).
- Vital signs, (Blood pressure, (BP), Heart Rate, (HR), Pulse, respirations and temperature).
- Weight.
- Complete Physical Exam.
- Targeted Physical Exam.
- ECG, (Day 1, Visits 4, 5, 6, 7, 8, 9, End of Study Visit 13, or Early termination).
- Blood & urine collection for safety laboratory testing, (including muscle enzymes).
- Males and females, (contraception check).
- All females Urine Pregnancy test.
- Blood collection for various biomarkers, (IP-10, MX-A, CCI hsCRP, Gene signature panel).
- CC
- **CC**
- Patient reported outcomes in the following order, PtGA, HAQ-DI, 5D Pruritus Scale,
 CCI
 FACIT-F, SF36 V2 Acute, and EQ-5D-5L,
 EQ-VAS.
- Recording of any new concomitant medications, DM concomitant medications or changes in ongoing concomitant medications.

- Collection for Viral Surveillance.
- Check for Infusion site reactions.
- Collection of any serious and non-serious adverse events.

6.2.4. Follow-up Visits for Stage 2

Due to the investigational drug's half-life of approximately 28 days, 5 follow-up visits, (Visits 6-10) will be conducted monthly. During the follow up period, the participant will have the following assessments and procedures completed. Please see Schedule of Assessments for specific details on which procedures will occur at each visit.

- Punch Skin biopsy (2), (Week 12, Visit 6).

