Appendix 1	l 6. List	t of Prohibited	and Permitted	Concomitant	Medications
------------	-----------	-----------------	---------------	-------------	-------------

Medications		C0251002	Follow-up Period
		Treatment Period Day 1-Week 12 (Stage 2)	-
		Treatment Period Day 1-Week 24 (Amended Stage 2 (Amended Stage 3)	
	I		
Corticosteroids	Parenteral injections (intra-articular) IA, IM, or IV)	Prohibited	Permitted
	Oral (prednisone or equivalent)	Permitted (Stage 2)	Permitted
		 Prednisone ≤15 mg/day or equivalent provided dose is stable for at least 30 days prior to Day 1. 	
		Permitted (Stage 3)	
		 Prednisone ≤20 mg/day or equivalent provided dose is stable for at least 30 days prior to Day 1. 	
		• Tapering of steroids is permitted after Week 24, in Amended Stage 2 and Stage 3.	
Immunosuppressive or immunomodulatory agents including methotrexate (MTX), azathioprine (AZA), leflunomide, mycophenolate (including mycophenolate mofetil, mycophenolate mofetil hydrochloride, and mycophenolate sodium), or 6-mercaptopurine (6-MP).		Permitted	Permitted
		• Provided pre-existing dose is stable for at least 60 days prior to Day 1.	
		• No new immunosuppressives or increase in dose is allowed during the treatment period.	
		• Participants can be on 1 of the following cytotoxic agents: MTX, AZA, leflunomide, mycophenolate, or 6-MP, but not on any combination of these cytotoxic agents.	
Antimalarials (eg, hydroxychloroquine, chloroquine, quinacrine)		Permitted	Permitted
		• Provided pre-existing dose is stable for at least 60 days prior to Day 1.	
		• No new antimalarial drugs or increase in dose is allowed during the treatment period.	
Thalidomide, tacrolimus, or mizoribine		Prohibited	Permitted
		• Any form of tacrolimus or any form of a topical calcineurin inhibitor, (TCI) is not allowed.	
Immunosuppressive topical		Permitted	Permitted
		• Immunosuppressive ointment for the scalp. Stable dose for 14 days prior to Day 1.	
Topical calcineurin inhibitors		Prohibited	Permitted
Immunosuppressive eye drops		Permitted	Permitted

Medications	C0251002	Follow-up Period
	Treatment Period Day 1-Week 12 (Stage 2)	_
	Treatment Period Day 1-Week 24 (Amended Stage 2	
	(Amended Stage 3)	
Investigational or marketed biologics (eg, abatacept, tocilizumab, TNF inhibitors)	Prohibited	Prohibited
Cyclophosphamide or chlorambucil	Prohibited	Permitted
Cyclosporine	Prohibited	Permitted
Other investigational drugs or investigational combinations	Prohibited	Prohibited

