2.2. Study Design

Initially, this was a multi-center Phase 2A study planned to be conducted in approximately 30 adult participants with moderate to severe DM. Thirty two participants were randomized in order to collect data from 24 participants who completed the study. Each participant was to take part in the study for a period of approximately 9 months. After the 35 day screening period, participants who were eligible enrolled into the study and were randomized in a blinded manner, 2:1 (Active:Placebo) ratio. Investigational drug or placebo administration took place on Day 1, Week 4, and Week 8 of the study. Participants then entered a 5-month follow-up period.

For Stage 2, with the addition of 1 lower dose 150 mg arm, this study then became a Phase 2, dose-finding double-blind, randomized, placebo-controlled study. Approximately 20 additional participants who meet eligibility criteria will be enrolled and randomly assigned in a blinded manner to receive PF-06823859 600 mg, 150 mg, or placebo dosed every 4 weeks according to a randomization ratio. 5:11:4. Participants will receive study drug, (active or placebo) on Day 1, Week 4, and Week 8 of the study and when treatment is completed all participants will enter a 5-month follow-up period.

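### For Stages 1 and 2 the protocol contradicts itself on whether the medication prohibitions end after Week 8 or at Week 12, and the planned censoring analyses may miss drugs started in between

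*Protocol*

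**What the plan says.** **End of treatment and start of follow-up, Stages 1 and 2**
- Protocol 6.2.1: "The treatment period will begin on Day 1 and consist of 4 scheduled visits, (Visits 2-5". Visit 5 is Week 8 in the Schedule of Activities.
- Protocol 6.2.4, headed for Stage 2: "5 follow-up visits, (Visits 6-10) will be conducted monthly". Visit 6 is Week 12, which Section 3.1 names as the primary endpoint visit.
- Protocol 3.1, for Stage 1, after listing the Day 1, Week 4 and Week 8 doses: "Participants then entered a 5-month follow-up period". SAP 2.2, for Stage 2: "when treatment is completed all participants will enter a 5-month follow-up period".

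**What follow-up changes**
- Protocol 5.9: "After a participant enters the follow up period, or prematurely withdrawn from the study for any reason, medically necessary treatments for DM will be allowed". It then adds: "The previous prohibited medications will no longer apply". No drug class is excepted.

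**Passages that point to Week 12**
- Appendix 16 heads its restricted column "Treatment Period Day 1-Week 12 (Stage 2" and does not name Stage 1. It permits parenteral steroids, kinase inhibitors and cyclophosphamide only in follow-up. It keeps biologics, B-cell depleting therapy, live vaccines and investigational drugs prohibited even then.
- Section 5.8.5 (corticosteroids) and exclusion criterion 12 in Section 4.2 (immunosuppressive, immunomodulatory and antimalarial agents, DMARDs) require stable doses through Week 12.
- Appendix 15 bars oral tacrolimus and topical calcineurin inhibitors for the length of the treatment period, without giving its end date.

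**Analysis**
- SAP 6.1.1.1 and 6.2.1.1 analyse observed values through Week 12 with LANCOVA-P. SAP 6.1.1.2 and 6.2.1.3 allow, but do not require, a repeat that censors visits after a participant meets the discontinuation criteria for prohibited medication.

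**The concern.** The term that switches the prohibitions off, entry into follow-up, has no single date in Stages 1 and 2. A site that reads 6.2.1 with 5.9 can treat the prohibitions as lifted after the Week 8 dose. A site that reads Appendix 16 keeps them to Week 12. The disputed interval lies immediately before the primary CDASI.

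A drug started in that interval could change the Week 12 score, and that score would enter the Stage 1 decision and the pooled estimates unadjusted. The censoring analysis may not find the case, for two reasons. A drug allowed by 5.9 is arguably not prohibited. And Appendix 14 acts on prohibited use by discontinuing treatment, but after Visit 5 no dose remains to discontinue in these stages, so the trigger may never be recorded.

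**Working it through.** **1. When does follow-up start?** Schedule of Activities days: Week 8 = Day 57, Week 12 = Day 85, Week 28 = Day 197.
- From Week 8: 197 − 57 = 140 days = 20 weeks.
- From Week 12: 197 − 85 = 112 days = 16 weeks.

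The protocol shows how it counts months. For Amended Stage 2, Section 3.1 calls Week 24 to Week 40 (16 weeks) 4 months and Week 20 to Week 40 (20 weeks) 5 months. On that convention the 5-month follow-up of Stages 1 and 2 runs from Week 8 to Week 28; a start at Week 12 would give 4 months. In calendar months (30.44 days) the two lengths are 4.6 and 3.7, which round the same way.

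The visit counts agree. Section 6.2.5 gives Amended Stage 2 four follow-up visits for its 4 months, the first 4 weeks after the treatment period ends. Five visits with the first at Week 12 imply a start at Week 8.

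**2. How long is the disputed interval?** Week 8 to Week 12 is 85 − 57 = 28 days on schedule. SAP Table 4 accepts Week 12 values up to Day 99, so it can reach 99 − 57 = 42 days.

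**3. Which drugs are affected?**
- Corticosteroids and background agents: 5.8.5 and exclusion 12 say Week 12, which conflicts with 5.9.
- Oral tacrolimus and topical calcineurin inhibitors: Appendices 15 and 16 both bar them, but Appendix 15 uses the undated term.
- Parenteral steroids, kinase inhibitors and cyclophosphamide: the bar during the study rests mainly on Appendix 16.
- Biologics, B-cell depleting therapy, live vaccines and investigational drugs: Appendix 16 keeps them prohibited in follow-up, and 5.9 makes no exception. This conflict exists whichever start date is meant.

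**4. What size could it have in Stage 1?** Inputs from Section 9.1.1: 16 active and 8 placebo completers, SD 8, true effect −8.6, 2-sided 90% interval.
- SE = 8 × √(1/16 + 1/8) = 3.464.
- The upper limit is below zero when the estimate is below −1.645 × 3.464 = −5.70, so the −5 condition does not bind.
- Probability of success = Φ(8.6/3.464 − 1.645) = Φ(0.838) = 79.9%, which reproduces the stated 80% (normal approximation).

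The documents give no rescue rate or rescue effect. Assumption: k of 8 placebo completers start a drug and each gains g units, nobody on active does, and the SD stays at 8. The placebo mean then moves by k × g / 8.
- k = 1, g = 5: 5/8 = 0.6. Effect −8.6 + 0.625 = −7.98; Φ(7.975/3.464 − 1.645) = Φ(0.657) = 74%.
- k = 2, g = 10: 20/8 = 2.5. Effect −8.6 + 2.5 = −6.1; Φ(6.1/3.464 − 1.645) = Φ(0.116) = 55%.

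**The case against.** The best case on the other side has four parts.

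- **Follow-up may begin at Visit 6.** No sentence dates entry to follow-up to the Week 8 dose, and five monthly visits could be what is meant by 5 months. The gap would then be zero and would agree with 5.8.5, exclusion 12 and Appendix 16. This reading is possible, and Figures 1 and 2, which might show the boundary, are not visible in the text reviewed. It fits less well with the protocol's own month count and with the SAP wording that follow-up starts when treatment is completed.
- **Other sections already protect Week 12.** This stands in part. A reader might infer that all the affected drugs depend on Appendix 16 alone. They do not: Appendix 15 also covers tacrolimus and topical calcineurin inhibitors, 5.8.5 is not limited to oral steroids, and adding an immunosuppressant is arguably a change under exclusion 12. These passages contradict 5.9, however; they do not settle which prevails.
- **Stage 1 is complete and ran under earlier protocol versions.** This stands. Rewording cannot change its conduct, and Section 6.2.4 and the Appendix 16 column name Stage 2 only. The Stage 1 case rests on 3.1 and 6.2.1 set against 5.8.5 and exclusion 12.
- **The SAP has other checks.** The per-protocol sensitivity analysis drops major deviations listed before unblinding, and all concomitant medications are listed. Both help, but whether a drug allowed by 5.9 counts as a deviation is the same open question.

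**Conclusion.** The contradiction is in the current text. The Week 8 reading is the better supported by the follow-up arithmetic, and the Week 12 reading by the medication sections. On the first, a dermatomyositis drug may be started in the 28 days before the primary CDASI, counted as observed, and missed by the censoring analyses.

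The effect on the result is unknown. Under the stated assumptions the Stage 1 placebo mean moves by 0.6 to 2.5 units and the probability of success falls from 80% to between 74% and 55%. If rescue is more frequent on placebo, the bias is towards no effect; equal use in both arms would offset much of it.

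Two stronger inferences are not supported. The documents do not show that any participant received such a drug, so the Stage 1 result cannot be called biased. And the −5 threshold belongs to the Stage 1 rule only: the pooled analysis, planned with about 11 placebo completers, has no hypothesis test, so a shift in that mean should not be set against 5.

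**What to change.** 1. **Reconcile the text.** Make Sections 3.1, 5.8.5, 5.9, 6.2.1 and 6.2.4, exclusion criterion 12 and Appendices 15 and 16 agree, with Stage 1 named, on when the prohibitions end and which persist in follow-up. This review does not say which rule is right.
2. **Add a start-date flag to SAP 6.1.1.2 and 6.2.1.3.** Whatever date is chosen, flag any new or increased dermatomyositis drug begun between Visit 5 and the Week 12 CDASI. In those sensitivity analyses, censor the values after its start date whether or not discontinuation criteria were recorded. Report the number flagged by arm and stage.

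The second step also works retrospectively for Stage 1 and original Stage 2, because Sections 5.8.1 and 5.8.5 already require start and stop dates for concomitant treatment. The cost is a wording clarification, one programmed flag and slightly fewer Week 12 values in a sensitivity analysis. The primary analysis is unchanged.
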